**Note: Non-irAEs will be managed as appropriate, following clinical practice recommendations.**

**8.2.1. Dose Modification and Toxicity Management of Infusion-reactions Related to Pembrolizumab**

Pembrolizumab may cause severe infusion-reactions including severe hypersensitivity or anaphylaxis. Dose modification and toxicity management guidelines on pembrolizumab associated infusion reaction are provided in [Table 5](#).

**Table 5: Pembrolizumab infusion reaction dose modification and treatment guidelines**

NCI CTCAE Grade	Treatment	Premedication at Subsequent Dosing
Grade 1  Mild transient reaction; infusion interruption not indicated; intervention not indicated	
 
May continue to receive pembrolizumab with close monitoring
 
	Premedication with antipyretic or antihistamine may be considered
Grade 2  Therapy or infusion interruption indicated but responds promptly to symptomatic treatment (e.g., antihistamines, NSAIDs, narcotics, IV fluids); prophylactic medications indicated for $\leq 24$ hrs.		
NCI CTCAE Grade	Treatment	Premedication at Subsequent Dosing
Grades 3 or 4  Grade 3:  Prolonged (i.e., not rapidly responsive to symptomatic medication and/or brief interruption of infusion); recurrence of symptoms following initial improvement;	
 
Stop Infusion. Subject is permanently discontinued from further study drug treatment.
 
	No subsequent dosing

hospitalization indicated for other clinical sequelae  Grade 4:  Life-threatening consequences; urgent intervention indicated		
Appropriate resuscitation equipment should be available at the bedside and a physician readily available during the period of drug administration. For further information, please refer to the Common Terminology Criteria for Adverse Events v5.0 (CTCAE) at http://ctep.cancer.gov		

### 8.2.2. Other Allowed Dose Interruptions for Pembrolizumab

Pembrolizumab may be interrupted for situations other than treatment-related AEs such as medical/surgical events and/or unforeseen circumstances not related to study therapy. Subjects should be placed back on study treatment within 3 weeks or 21 days of originally scheduled dose and within 42 days of previously administered dose, unless otherwise discussed with and approved by the Sponsor. The reason for interruption should be documented in the subject's study record.

## 9. Concomitant Therapy

Medications or vaccinations specifically prohibited in the exclusion criteria are not allowed during the ongoing study. If there is a clinical indication for any medication or vaccination specifically prohibited during the study, discontinuation from study treatment or vaccination may be required. The investigator should discuss any questions regarding this with the Sponsor or Sponsor's assigned designee. The final decision on any supportive therapy or vaccination rests with the investigator and/or the subject's primary physician. However, the decision to continue the subject on study treatment requires the mutual agreement of the investigator, the Sponsor and the subject.

### 9.1. Prohibited Medications/Treatment

- Antineoplastic systemic chemotherapy or biological therapy
- Immunotherapy not specified in this protocol
- Chemotherapy not specified in this protocol
- Investigational agents other than NT-I7 and pembrolizumab
- Radiation therapy  
*Note: Radiation therapy to a symptomatic solitary lesion or to the brain may be allowed at the investigator's discretion.*
- Live/attenuated vaccines within 30 days prior to the first dose of study treatment and while participating in the study up to 90 days following the last dose of study drug. Examples of live vaccines include, but are not limited to, the following: measles, mumps, rubella, varicella/zoster, yellow fever, rabies, BCG, and typhoid vaccine. Seasonal influenza vaccines for injection are generally killed virus vaccines and are allowed; however, intranasal influenza vaccines (e.g., FluMist®) are live attenuated vaccines and are not allowed.
- Systemic glucocorticoids are permitted only for the following purposes:
  - To modulate symptoms of an AE that is suspected to have an immunologic etiology
  - Short-term oral or IV use in doses >10mg/day prednisone equivalent for the prevention of emesis is allowed after discussion with and approval by the Medical Monitor
  - Premedication for IV contrast allergies
  - Short-term oral or IV use in doses >10mg/day prednisone equivalent for COPD exacerbations
  - For chronic systemic replacement not to exceed 10 mg/day prednisone equivalent
  - In addition, the following glucocorticoid use is allowed:
    - For topical use or ocular use
    - Intra-articular joint use
    - For inhalation in the management of asthma or chronic obstructive pulmonary disease.

*Note: Inhaled steroids are allowed for management of asthma.*

- Immunostimulatory and immunosuppressive agents are prohibited.

Subjects who, in the assessment of the investigator, require the use of any of the aforementioned treatments for clinical management should be removed from the study.

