7. History of severe hypersensitivity reactions to monoclonal antibodies (mAbs) or intravenous immunoglobulin preparations; any history of anaphylaxis; prior history of human anti-human antibody response; known allergy to any of the study medications, their analogues, or excipients in the various formulations of any agent.  
**Note:** Subjects with severe hypersensitivity ( $\geq$ Grade 3) to pembrolizumab and/or any of its excipients are also excluded.
8. Subjects who have spinal cord compression not definitively treated with surgery and/or radiation or previously diagnosed and treated spinal cord compression without evidence that disease has been clinically stable for  $\geq$ 2 weeks prior to screening.
9. Subjects who have autoimmune disease history for the past 2 years, including but not limited to systemic lupus erythematosus, rheumatoid arthritis, inflammatory bowel disease, vascular thrombosis associated with antiphospholipid syndrome, Wegener's granulomatosis, Sjögren's syndrome, Bell's palsy, Guillain-Barre syndrome, multiple sclerosis, vasculitis or glomerulonephritis.
10. Have active and clinically relevant bacterial, fungal, viral, or TB infection, including known Hepatitis A, B, or C or HIV (testing not required).
11. Clinically significant cardiac disease, including, but not limited to, any of the following: Congestive heart failure requiring treatment (New York Heart Association Grade  $\geq$  2); clinically significant and uncontrolled atrial fibrillation; history of acute coronary

syndromes including myocardial infarction, unstable angina, coronary artery bypass grafting, coronary angioplasty, or stenting < 6 months prior to screening; symptomatic chronic heart failure, history or current evidence of clinically significant cardiac arrhythmia and/or conduction abnormality < 6 months prior to screening except controlled atrial fibrillation and paroxysmal supraventricular tachycardia.

12. Subjects who have received treatment with systemic immunosuppressive medications (including, but not limited to, systemic prednisone >10 mg/day or its equivalent, cyclophosphamide, azathioprine, methotrexate, thalidomide and antitumor necrosis factor [anti-TNF] agents) within 7 days prior to first dose of study treatment.

*Note: Replacement therapy (e.g., thyroxine, insulin, or physiologic corticosteroid replacement therapy for adrenal or pituitary insufficiency) is not considered a form of systemic treatment and is allowed.*

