## V7.0 incorporating Amendment 6, 26Oct2023

**Note:** Subjects with RECIST-defined progressive disease (PD) who are otherwise stable without symptomatic progression should continue study treatment until the next radiographic imaging time point (at least 4 weeks after the prior assessment of PD) to assess for possible pseudo-progression.

Discontinuation from treatment does not represent withdrawal from the trial.

Subjects may discontinue treatment at any time for any reason or be dropped from treatment at the discretion of the Investigator, should any untoward effect occur. In addition, a subject may be discontinued from treatment by the Investigator or the Sponsor, if treatment is inappropriate, the trial plan is violated, or for administrative and/or other safety reasons.

A subject may be discontinued from treatment but continue to be monitored in the trial for any of the following reasons:

- The subject or subject's legally acceptable representative requests to discontinue treatment
- The Investigator believes that for safety reasons or tolerability reasons (e.g., AE) it is in the best interest of the subject to discontinue study drug.
- Intercurrent illness that prevents further administration of treatment
- Unacceptable AEs (e.g., those meet the DLT criteria or other adverse events which can jeopardize patient safety per enrolling physician or considered unacceptable by the subject)
- Progressive disease confirmed radiographically.
  - *Note: In the case of suspected pseudoprogression, patients will be advised to continue treatment beyond initial RECIST 1.1-defined PD while waiting for confirmation of PD, provided they are clinically stable (per iRECIST). Investigators are recommended to consult with the Sponsor designee regarding individual cases.*
  - Treatment interruption lasting >12 weeks (see Section [8.1.1](#))
  - The patient becomes pregnant. Refer to Section [11.8](#).
  - Noncompliance with study procedure requirements or study drug administration (e.g., non-compliance with study visits and miss too many drug administrations).
  - The subject persistently uses a disallowed medication as discussed with the Sponsor's designee.
  - Discontinuation of treatment may be considered, at the discretion of the treating physician per criteria below, but continue to be monitored in the study for any of the following reasons:
    - Recurrent Grade 2 pneumonitis

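### Protocol Section 9.1 removes subjects who need a prohibited treatment from the study, and exempts only glucocorticoids for immune-related AEs, contrary to the protocol's own follow-up rules and irAE guidance (minor)

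*Protocol*

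**What the plan says.** Section 9.1 of the protocol lists prohibited treatments and closes by saying that subjects who, in the investigator's assessment, "require the use of any of the aforementioned treatments for clinical management should be removed from the study". Within the list, systemic glucocorticoids have several permitted uses, one of which is "To modulate symptoms of an AE that is suspected to have an immunologic etiology". The last item in the list has no such exception: "Immunostimulatory and immunosuppressive agents are prohibited".

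The lead-in to Section 9 is milder. If a prohibited medication or vaccination is clinically indicated, "discontinuation from study treatment or vaccination may be required".

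Section 6.4.1 separates stopping treatment from leaving the trial. It introduces a list with "A subject may be discontinued from treatment but continue to be monitored in the trial for any of the following reasons", and one item on that list is "The subject persistently uses a disallowed medication". Section 6.4.2 gives four reasons for withdrawal from the study: failing eligibility, withdrawn consent, loss to follow-up and death. Section 6.6 orders survival follow-up every 90 days once new anticancer treatment starts. Footnote 28 of Section 7.4 has those calls record new anticancer treatments.

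On irAEs, Section 8.1 names mycophenolate and TNF-alpha antagonists, alongside corticosteroids, for severe cases. Table 4 allows other systemic immunosuppression when corticosteroids do not control the event, both in its general instructions and in its row for all other irAEs.

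**The concern.** Two rules in operative text give different instructions for the same subject. A site that reads Section 9.1 literally takes a subject who needs a listed treatment off study. A site that reads Sections 6.4.1 and 6.6 stops study treatment if necessary and keeps the subject in follow-up. Likewise, a site that treats a steroid-refractory irAE as Table 4 suggests is using an agent that Section 9.1 prohibits, which then triggers the removal sentence.

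What is at stake is scheduled follow-up: tumor scans, the day-30 and day-90 safety visits, and survival contact. Data on progression-free survival (PFS), duration of response (DoR) and overall survival (OS), and on late safety, could then depend on which section a site happened to follow.

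**Working it through.** No arithmetic applies: the plan states no figure on this point. The check is to set the sections side by side and then ask which subjects are exposed.

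**Conflict 1: off study or off treatment**

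| Source | Consequence of needing or using a prohibited treatment |
|---|---|
| Section 9.1, closing sentence | Removal from the study |
| Section 9 lead-in | Study treatment may have to stop |
| Section 6.4.1 | Persistent use is a reason to stop treatment while monitoring continues |
| Section 6.4.2 | Not among the four reasons for study withdrawal |
| Section 6.6; Section 7.4, footnote 28 | Survival follow-up continues after new anticancer therapy, and that therapy is recorded |

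Section 9.1 stands alone. It cannot be squared with footnote 28, which expects to collect the very treatments that would have ended participation. The choice of words has consequences, because Section 6.4.2 says a subject who withdraws from the trial is no longer followed at scheduled visits.

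**Conflict 2: immunosuppressants for irAEs**

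- Section 9.1 prohibits the class and gives its immune-AE exception to glucocorticoids only. It does not mention irAEs in the immunosuppressant item. The absence of an exception follows from setting that item beside the glucocorticoid one.
- Section 8.1 and Table 4 allow non-steroid agents for severe or steroid-refractory irAEs.
- These cannot both apply unless Section 9.1 carries an exception that it does not state.

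**Who is exposed**

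1. *Subjects who start new anticancer therapy.* Section 6.6 expressly orders survival follow-up. Disease assessment ends at that point anyway under Sections 6.6 and 13.3, and SAP Table 4 censors PFS and DoR at the last adequate assessment before the new therapy. Little is left beyond the safety visits.
2. *Subjects taken off for an unacceptable adverse event, including an irAE.* Sections 6.4.1 and 6.6 say they are followed until the event resolves or stabilizes, and for disease status and survival.
3. *Everyone else who meets the Section 9.1 trigger.* Examples are a live vaccine, an immunosuppressant for a condition that is not an adverse event, or an immunosuppressant for an irAE that calls for withholding rather than stopping study treatment. No express sentence protects these subjects. They rely on the general rules in Sections 6.4.1 and 6.6 and footnote 28, which a literal reading of Section 9.1 would override.

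Group 3 is where follow-up could be lost. For these subjects PFS and DoR would be censored at the last adequate assessment (SAP Section 4.9.4.3) and OS at the last known alive date (SAP Section 4.9.4.4). All three are secondary endpoints analyzed descriptively.

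**The case against.** The strongest reply is that Section 9.1 is simply loose. Sections 6.4.1 and 6.6 themselves speak of subjects being removed from study for adverse events and, in the same sentence, order that they be followed. Against that usage and several explicit passages, a sensible site would read Section 9.1 as removal from treatment. Section 8.2 also makes the pembrolizumab guidance the rule for managing any adverse event, so the specific irAE table can be said to prevail over a general list. Most of this stands, and it is why the point is minor. It does not remove the contradiction: the adverse-event sentences carry their own follow-up instruction and Section 9.1 carries none.

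A reader might infer more than the documents support:

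- *That irAE care is blocked.* It is not. Section 9 leaves supportive therapy to the investigator or primary physician, and allows study treatment to continue by mutual agreement with the Sponsor and subject. Section 9.2 permits treatment needed for the subject's welfare.
- *That exclusion criterion 12 reinforces the ban*, because it names "cyclophosphamide, azathioprine, methotrexate, thalidomide and antitumor necrosis factor [anti-TNF] agents" and Section 9 says "Medications or vaccinations specifically prohibited in the exclusion criteria are not allowed during the ongoing study". This is weak. The criterion is a 7-day pre-dose washout that also covers prednisone above 10 mg/day, while Section 9.1 permits systemic glucocorticoids on study for immune events. A literal carry-over cannot be intended.
- *That Section 10 adds a further conflict.* It refers to additional anti-inflammatory agents and names no immunosuppressant.
- *That Section 9.1 bars a resumption which Table 4 allows.* Table 4 speaks of resuming pembrolizumab after a corticosteroid taper. Neither it nor Section 8.1.1 expressly permits resumption after a non-steroid immunosuppressant.

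**Conclusion.** Section 9.1 is wrong as written on both counts, and the severity is minor. The contradiction is certain from the text. The harm depends on a site following Section 9.1 literally, and falls mainly on subjects outside the two express follow-up provisions.

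The size of the effect cannot be estimated. The documents give no rate of prohibited-treatment use before progression, no rate of steroid-refractory irAEs, and nothing on how sites read Section 9.1. One could count the scans, visits and calls scheduled in the first year off treatment, but that would describe the schedule, not what would be lost or its effect on any estimate. A reader might also infer a bias in OS of some stated size; the documents give nothing from which to derive one. No effect on the objective response rate, the Simon two-stage design, the Go/No Go decision or the sample size is claimed.

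**What to change.** Make two wording changes in Section 9.1, by protocol amendment or site clarification letter:

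1. Replace the removal phrase with: *should be discontinued from study treatment where required and followed per Sections 6.4.1 and 6.6*.
2. Add to the immunosuppressant item: *except when used to manage irAEs per Section 8.1 and Table 4*. Resumption of study treatment stays governed by Section 8.1.1 and Table 4.

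The cost is the text change. No visits, scans or calls are added, because those involved are already scheduled, and the change does not widen the irAE treatments the protocol already allows.

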## 9.2. Medications Used with Caution

No data exist regarding the interaction of NT-I7 with drugs known to prolong the QT/QTc interval. Accordingly, subjects receiving these drugs while receiving NT-I7/pembrolizumab therapy should be closely monitored.

No data exist regarding the interaction of NT-I7 with commonly used vitamins, minerals, supplements, herbal and natural remedies. Accordingly, these drugs should be avoided, or used with caution at the investigator's discretion, and closely monitored while the subject is receiving the study treatment.

All treatments that the investigator considers necessary for a subject's welfare may be administered at the discretion of the investigator in keeping with the community standards of medical care. For example, subjects can continue using medically prescribed marijuana/ Marinol for purposes such as cancer related fatigue, nausea, vomiting, appetite improvement etc. while participating in the study.

*All concomitant medications will be recorded on the eCRF including all prescription, over-the-counter (OTC) products, herbal supplements, and IV medications and fluids. If changes occur during the study period, documentation of drug dosage, frequency, route, and date should also be included on the eCRF.*

All concomitant medications received within 7 days prior to the first dose of study treatment and up to 30 days after the last dose of study treatment should be recorded. Concomitant medications administered 30 days after the last dose of study treatment should be recorded for SAEs and events of special interest or clinical interest (ECIs) as defined in Sections **11.4** and **11.6**.

## 10. Rescue Medications and Supportive Care

Subjects should receive appropriate supportive care measures as deemed necessary by the treating investigator. Suggested supportive care measures for the management of AEs with potential immunologic etiology are outlined along with the dose modification guidelines in Section **8**. ([Table 4](#)). Where appropriate, these guidelines include the use of oral or IV treatment with corticosteroids, as well as additional anti-inflammatory agents if symptoms do not improve with administration of corticosteroids. Note that several courses of steroid tapering may be necessary as symptoms may worsen when the steroid dose is decreased. For each disorder, attempts should be made to rule out other causes such as metastatic disease, or bacterial or viral infection, which might require additional supportive care. The treatment guidelines are intended to be applied when the investigator determines the events to be related to pembrolizumab.

**Note:** If after the evaluation of the event, it is determined not to be related to pembrolizumab, the investigator does not need to follow the treatment guidance. Refer to [Table 4](#) in Section **8** for guidelines regarding dose modification and supportive care.

It may be necessary to perform conditional procedures such as bronchoscopy, endoscopy, or skin photography as part of evaluation of the event.

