### 8.1. Dose Modification of NT-I7

Clinical experience has demonstrated that development of autoimmune inflammatory conditions is a general risk with therapeutics intended to enhance anti-tumor T-cell responses. Such irAEs have been described for virtually all organ systems and include, but are not limited to, colitis, hepatitis, pneumonitis, endocrinopathy, ocular toxicity, pancreatic toxicity, and rash.

Risks of autoimmunity associated with NT-I7 are theoretical and yet not fully evaluated in the clinical setting. Due to this potential risk of NT-I7 to induce autoimmune conditions, subjects with a history of autoimmune disease will be excluded from this study.

The risk of development of autoimmune inflammatory condition related to NT-I7 seems relatively low. None of the irAEs were reported in previous clinical studies with rhIL-7, or with NT-I7 including the FIH study completed in normal healthy individuals, and solid tumor subjects (Study No. GX-I7-HV-001 and Study No. GX-I7-CA-003).

Nevertheless, however, given the limited clinical experience with NT-I7, immune-related toxicities associated or possibly associated with NT-I7 should be closely monitored and carefully managed according to standard medical practice (e.g., thyroid hormone replacement for autoimmune hypothyroidism). Additional tests, such as autoimmune serology or biopsies, should be used to determine a possible immunogenic etiology. Although most irAEs observed with immune modulatory agents have been mild and self-limiting, such events should be recognized early and treated promptly to avoid potential major complications ([69](#)).

Discontinuation of NT-I7 may not have an immediate therapeutic effect, and there is no available antidote for NT-I7. The primary approach to mild irAEs (Grades 1–2) is supportive and symptomatic care. In severe cases, irAEs may be acutely managed with systemic corticosteroids, mycophenolate or TNF- $\alpha$  antagonists ([40](#), [69-85](#)).

Dose modifications of NT-I7 for Adverse Events: AEs from NT-I7 are expected to be mild and infrequent, transient and Grade 2 or less (as noted in the AE list, Section [11.1.1](#)). If a subject experiences a clinically significant and/or unacceptable toxicity, dosing should be interrupted, or reduced or discontinued (see below for detailed guidance), and supportive therapy administered per standard clinical practice.

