## 8.2. Dose Modification of Pembrolizumab

The toxicity of pembrolizumab could be accentuated by administration of NT-I7 and the component attributable to pembrolizumab and NT-I7 will be difficult if not impossible to sort out. Thus, the management of pembrolizumab will be used for the treatment of any AE. NT-I7 treatment will be discontinued when pembrolizumab must be **permanently discontinued**.

AEs associated with pembrolizumab exposure may represent an immune-related response. These irAEs may occur shortly after the first dose or several months after the last dose of pembrolizumab treatment and may affect more than one body system simultaneously. Therefore, early recognition and initiation of treatment is critical to reduce complications. Based on existing clinical study data, most irAEs were reversible and could be managed with interruptions of pembrolizumab, administration of corticosteroids and/or other supportive care. For suspected irAEs, ensure adequate evaluation to confirm etiology or exclude other causes. Dose modification and toxicity management guidelines for irAEs associated with pembrolizumab are provided in [Table 4](#).

When study interventions are administered in combination, attribution of an adverse event to a single component is likely to be difficult. Therefore, while the investigator may attribute a toxicity event to the combination, to NT-I7 alone, or to pembrolizumab alone, for adverse events listed in [Table 4](#), both interventions must be held according to the criteria in .

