### *Holding Study Interventions:*

When study interventions are administered in combination, if the AE is considered immune-related, both interventions should be held according to recommended dose modifications.

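### For immune-related events attributed to NT-I7 alone, Protocol Section 10 waives the Table 4 treatment guidance that Section 8.2 applies whichever drug is blamed

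*Protocol*

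**What the plan says.** **Section 10 (Rescue Medications and Supportive Care)** points to Table 4 for managing events of possible immune origin and then limits its use: "The treatment guidelines are intended to be applied when the investigator determines the events to be related to pembrolizumab". The Note that follows says that if, after evaluation, "it is determined not to be related to pembrolizumab, the investigator does not need to follow the treatment guidance". It then sends the reader to Table 4 "for guidelines regarding dose modification and supportive care".

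**Section 8.2 (Dose Modification of Pembrolizumab)** starts from the premise that the share of a toxicity due to each drug can hardly be sorted out, and concludes that "the management of pembrolizumab will be used for the treatment of any AE". It goes on to say that, "while the investigator may attribute a toxicity event to the combination, to NT-I7 alone, or to pembrolizumab alone", for events listed in Table 4 "both interventions must be held according to the criteria in" what is evidently that table. The paragraph on holding treatment repeats the rule: "if the AE is considered immune-related, both interventions should be held according to recommended dose modifications". The paragraph on restarting covers toxicity attributed to NT-I7 alone. A note after Table 4 leaves events that are not immune-related to clinical practice.

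**Section 8.1 (Dose Modification of NT-I7)** states: "The primary approach to mild irAEs (Grades 1–2) is supportive and symptomatic care". It mentions systemic corticosteroids as an option in severe cases, without a dose. It also withholds NT-I7 for a related Grade 2 event.

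**The concern.** Section 10 makes treatment depend on an attribution that Section 8.2 says cannot be made reliably. An investigator who judges a Grade 2 pneumonitis to be caused by NT-I7 and not by pembrolizumab can find support in one section for setting Table 4 aside, and an instruction in another to use it.

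The case can arise. Section 8.2 expects attribution to NT-I7 alone, and SAP Section 4.11.2 tabulates NT-I7-related and pembrolizumab-related events separately.

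What is at stake is patient safety and consistent management across sites, specifically whether the Table 4 steroid course and taper are given. Section 8.2 itself warns that NT-I7 could worsen pembrolizumab toxicity. Section 2.4.1.3 reports two fatal myocarditis events with NT-I7 plus a checkpoint inhibitor, for which a contribution from NT-I7 is not excluded. Instructions on immune toxicity should not contradict each other in this setting.

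**Working it through.** The plan gives no figure to reproduce. The check sets the instructions side by side.

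**Step 1: where the sections overlap.** Read alone, the Section 8.2 sentence on pembrolizumab management covers every adverse event. The note after Table 4 removes events that are not immune-related, the must-hold rule is confined to events listed in Table 4, and the holding paragraph is confined to immune-related events. Section 10 releases events judged unrelated to pembrolizumab. The overlap is therefore immune-related events attributed to NT-I7 and not to pembrolizumab.

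**Step 2: a worked case.** Take Grade 2 colitis attributed to NT-I7 alone.

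| Source | NT-I7 | Pembrolizumab | Corticosteroids |
|---|---|---|---|
| Section 8.2 with Table 4 | Hold | Hold | 1 to 2 mg/kg prednisone or equivalent, then taper |
| Section 10 | Treatment guidance optional | Treatment guidance optional | Treatment guidance optional |
| Section 8.1 and 8.1.1 | Withhold; resume once colitis is back to baseline | Not addressed | No dose; supportive care for Grades 1–2, steroids possible if severe |

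The Section 10 row does not say that the holds are waived. How far its release extends is taken up under the objection. The steroid column differs on any reading.

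**Step 3: how much of Table 4 is affected.** The event groups are pneumonitis, colitis, hepatitis, type 1 diabetes or hyperglycemia, adrenal insufficiency and hypophysitis, hyperthyroidism, hypothyroidism, nephritis, severe skin reactions (counted once), and all other immune-related events, which makes 10. Those with a weight-based steroid dose at Grade 2 are:

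- pneumonitis: 1 to 2 mg/kg
- colitis: 1 to 2 mg/kg
- hepatitis: 0.5 to 1 mg/kg
- nephritis: 1 to 2 mg/kg

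That is 4 of 10. The group for all other immune-related events calls for steroids according to severity above Grade 1. Adrenal insufficiency and hypophysitis lists steroids at Grade 2 without a weight-based dose. Neither is counted.

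**Step 4: how often this might arise.** Section 8.1 says that no immune-related events were reported in earlier rhIL-7 studies or in the healthy-volunteer and solid-tumor studies of NT-I7. That suggests few such events would be attributed to NT-I7 alone. The two NT-I7 studies named there gave it without a checkpoint inhibitor, so this is an indication and not a rate for the combination.

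**Step 5: does the proposed wording remove the conflict?** With relatedness to either drug as the test, an event attributed to NT-I7 alone falls under Table 4 in both sections. Section 10 would still release events related to neither drug. Section 11.4 defines an immune-related event as one associated with drug exposure with no clear other cause, so the events still released should not be immune-related ones.

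**The case against.** The best defence is that the Note was never meant for NT-I7 toxicity. It comes shortly after advice to rule out metastatic disease and infection, so it may simply release events with a non-drug cause. Section 10 also calls its measures suggestions and leaves supportive care to the treating investigator. This is plausible as to intent, but the test written is relatedness to pembrolizumab, and an event attributed to NT-I7 alone meets the release on its plain words.

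Three stronger readings are tempting, and the documents do not support them:

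- **That the conflict covers any adverse event.** The note after Table 4 leaves events that are not immune-related to clinical practice.
- **That Section 10 leaves the site with Section 8.1 only.** Section 8.2 remains in force, so the site has two conflicting instructions, not a void. Section 8.1 also offers more than supportive care: NT-I7 is withheld at related Grade 2, any grade of myocarditis ends NT-I7, and Section 8.1.1 presupposes steroid tapers in its criteria for resuming. What it lacks is a steroid dose.
- **That Section 10 also waives the hold and discontinuation rules.** The Note's reference to Table 4 covers dose modification, so a site could read it that way, but the release itself speaks only of treatment guidance. The reading is possible but not compelled, and the priority given here does not rest on it.

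Other controls limit harm. Section 6.4.1 makes toxicities that call for permanent discontinuation under Section 8.2 a reason to consider stopping treatment. Section 7.2 sends immediate safety concerns to the Sponsor. Immune-related events are of special interest under Section 11.4 and reportable within 24 hours under Section 11.3. Section 9.1 permits steroids for a suspected immune event. These controls stand, but none of them tells the site to give the Table 4 course.

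**Conclusion.** The contradiction is real and narrow. For immune-related events attributed to NT-I7 and not to pembrolizumab, Section 10 makes the Table 4 treatment guidance optional while Section 8.2 applies it and holds both drugs. The sharpest consequence is at Grade 2 in the four event groups where Table 4 sets a weight-based steroid dose.

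This rests on reading Section 10 by its words and on investigators recording attribution drug by drug. The number of patients affected is unknown. It is probably small, as an inference from the earlier studies and not a figure in the plan. The response endpoints, sample size, error rates and analyses are untouched. It is a low-priority safety wording correction.

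**What to change.** In both Section 10 sentences, replace *related to pembrolizumab* with *related to study treatment (NT-I7 and/or pembrolizumab)*. Optionally add: *This Note does not waive the Section 8.2 and Table 4 hold and discontinuation rules for immune-related events.*

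Do not go further and add a rule that the stricter of Sections 8.1 and 8.2 applies to each drug. Neither section contains such a rule, and it would be ambiguous. For Grade 2 hypothyroidism related to NT-I7, Section 8.1 withholds NT-I7 while Table 4 continues pembrolizumab, and the added rule could be read as stopping both.

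The cost is two wording changes and at most one added sentence at the next amendment, with no change to data collection, sample size or the SAP.
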